2.2 Aims and Hypotheses

2.2.1 Aim 1: Determine if our intervention leads to decreases in BP.

2.2.1.1 Hypothesis: Mean systolic BP in the pharmacist-intervention group will be significantly lower than mean systolic BP in the control group at 6 and 12 months.

2.2.1.2 Hypothesis: Mean diastolic BP in the pharmacist-intervention group will be significantly lower than mean diastolic BP in the control group at 6 and 12 months.

2.2.2 Aim 2: Determine if our intervention leads to intensification of therapy.

2.2.2.1 Hypothesis: Participants in the pharmacist-intervention group will have more treatment changes, on average, than those in the control group.

2.2.3 Aim 3: Determine the cost effectiveness of the intervention.

2.2.3.1 Hypothesis: The intervention will be cost effective when compared to the control group.

3. Subject Inclusion/Exclusion Criteria

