The pharmacists will review the home BP values with the intervention subjects. If the home BP values are controlled, the pharmacist will continue to monitor home BP values.

However, if the pharmacist identifies issues such as poor medication adherence, inability to afford medications or other issues, they will work with the patient and physician to optimize therapy and/or reduce cost. If the pharmacist suspects white coat hypertension, they will make a recommendation to the physician to refer the patient to the University of Iowa ambulatory blood pressure service.

If BP values are elevated, the pharmacist will assess medication adherence, ability to pay for medications and whether the regimen is optimal to control BP based on patient demographics and co-existing conditions. The pharmacist will communicate recommendations for lifestyle and other changes directly to the subject. If medication changes are needed, the pharmacist will communicate to the physician through the electronic medical record. The pharmacist may recommend:

1. Increased dose of a medication.
2. Addition of a medication.
3. Discontinuation of a medication.
4. Modification of the regimen to optimize therapy, improve convenience (e.g. fixed-dose combinations) or reduce cost.

All participants in the pharmacist intervention group will continue to have access to a research pharmacist for the entire 12 months of follow up. Additionally, they will be asked to continue measuring and texting BP values (1 morning, 1 evening) for 3 days each month throughout the 12-month follow up.

The pharmacists will typically contact with the participants every 2 weeks while BP is not controlled. Once BP is controlled, they will continue monitoring the participant's records and home BPs and make contact at least every 2 months to support adherence and reassess BP control.

The REDCap forms that the pharmacists will use to record data are shown in Appendix 10

4.5 6-Month Visit Procedures

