Aim 1 Analysis: The analysis will be done on an intent-to-treat basis regardless of the number of reported BP readings or the number of pharmacist interactions with the participant. Our primary outcome will be a comparison of mean SBP values at 12 months. We will use linear mixed effects models (LMMs) with BP as the outcome. We will explore the timing of the change by also evaluating BP at 6 months. To test the intervention, we will include time (baseline, 6 month, 12 month) as a fixed effect factor and its interaction with treatment arm. We will use random effects for clinic and physician nested within clinic to account for practice heterogeneity between clinics and providers. Temporal correlation will be accounted for by using an autoregressive error structure. Specifically, the model will be given as

$$\begin{aligned}
 BP_{cpit} &= \tau_t + \alpha_c + \gamma_{cp} + (\omega_t + \nu_{tc} + \xi_{tcp})X_{cpi} + \epsilon_{cpit}, \\
 c &= 1, \dots, C, \quad p = 1, \dots, P_c, \quad i = 1, \dots, n_{cp}, \quad t \in \{0, 6, 12\}, \\
 (\alpha_c, \gamma_{cp})' &\stackrel{\text{iid}}{\sim} N(0, G_1), \\
 (\nu_{0c}, \nu_{6c}, \nu_{12c})' &\stackrel{\text{iid}}{\sim} N(0, G_2), \\
 (\xi_{0cp}, \xi_{6cp}, \xi_{12cp})' &\stackrel{\text{iid}}{\sim} N(0, G_3), \\
 (\epsilon_{cpio}, \epsilon_{cpis}, \epsilon_{cpis})' &\stackrel{\text{iid}}{\sim} N(0, R),
 \end{aligned}$$

where C is the number of clinics, P_c is the number of providers within the c^{th} clinic, n_{cp} is the number of subjects recruited under the p^{th} provider in the c^{th} clinic, $BP_{(cpit)}$ is the blood pressure at time t for the i^{th} subject under the p^{th} provider within clinic c , τ_t is the control mean at time t , α_c and γ_{cp} are the random control effects for the clinic and provider-nested-within-clinic respectively, ω_t is the treatment effect at time t , ν_{tc} and ξ_{tcp} are the random treatment effects for the clinic and provider-nested-within-clinic respectively, X_{cpi} equals 1 if the i^{th} subject under the p^{th} provider within clinic c is assigned to the treatment group and zero otherwise, ϵ_{cpit} is the (auto-correlated) noise term, and G_1 , G_2 , G_3 , and R are covariance matrices for the random effects. This model will also be estimated for DBP.

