Second, transition to control for patients who were uncontrolled at their baseline visit will be modeled using a generalized linear mixed effects model (GLMM) based on the Bernoulli distribution with a logistic link. We will test the intervention by including a fixed-effects term for the treatment assignment (intervention versus control). As before, we will include random effects for provider nested within clinic. Specifically, the model will be

$$\begin{aligned}
 \text{logit}(\mathbb{P}(Z_{cpio} = 1 | Z_{cpis} = 0)) &= \tau + \alpha_c + \gamma_{cp} + (\omega + \nu_c + \xi_{cp})X_{cpi}, \\
 (\alpha_c, \gamma_{cp})' &\stackrel{\text{iid}}{\sim} N(0, G_1), \\
 (\nu_c, \xi_{cp})' &\stackrel{\text{iid}}{\sim} N(0, G_2),
 \end{aligned}$$

where Z_{it} equals 1 if the i^{th} subject under the p^{th} provider within clinic c is controlled at time t , $t \in \{0, 6\}$, and zero otherwise.

Third, we will assess the duration of the change by modeling the odds of having controlled BP at 12 months among those uncontrolled at baseline but controlled at 6 months using a GLMM similar to that described above. All three models will contain any covariates (e.g., age, sex) that were not sufficiently addressed through randomization. In all analyses, the random effects incorporated into the final model will be chosen via Akaike Information Criterion with correction for small sample sizes (AICc).

Power: Based on prior work with the CAPTION trial, we expect a mean decrease in SBP of 17.3 (SD = 17.7) mmHg in the intervention arm and a decrease of 11.6 (SD = 18.2) mmHg in the control arm. We expect a difference of 5.65 mmHg between the groups with an expected pooled standard deviation of 17.9 with equal sized groups. In order to have 90% power to detect a difference of 5.7 mmHg or larger decrease in SBP with a Type I error rate of 5% and a standard deviation of 17.9 mmHg, we would need 180 subjects per arm or 360 subjects total.

In preliminary work in the CAPTION trial, 13.4% of control subjects dropped out or were lost to follow-up. 14.0% of subjects dropped out of the intervention arm during the first 9 months. In order to retain power after reasonable attrition rates over 12 months, we will recruit an additional 14% in each group to ensure we have at least 85% power. In addition, the sample size should be slightly increased to accommodate the interim analyses. This increases our total sample size to 420.

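### The supporting Aim 1 durability model compares the arms only among participants controlled at 6 months, so its odds ratio is not a randomised comparison and is open to selection bias of uncertain direction

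*Combined protocol and SAP*

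**What the plan says.** Section 6 (Aim 1 Analysis) has three models.

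- **First:** a linear mixed model for blood pressure at 0, 6 and 12 months, with a separate treatment effect ω at each time. It is not conditioned on any follow-up response.
- **Second:** a logistic mixed model for transition to control among those uncontrolled at baseline, with a fixed effect for randomised arm. Its time index covers only months 0 and 6.
- **Third:** "Third, we will assess the duration of the change", done by "modeling the odds of having controlled BP at 12 months among those uncontrolled at baseline but controlled at 6 months", with a model like the second.

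Four other statements bear on the third model.

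- Aim 1 opens with: "The analysis will be done on an intent-to-treat basis regardless of the number of reported BP readings" or of pharmacist contacts. No exception is made for the third model.
- Adjustment is limited as follows: "All three models will contain any covariates (e.g., age, sex) that were not sufficiently addressed through randomization".
- Section 2.2 hypothesises: "Mean systolic BP in the pharmacist-intervention group will be significantly lower than mean systolic BP in the control group at 6 and 12 months".
- Section 4.4.2 says intervention participants "will continue to have access to a research pharmacist for the entire 12 months of follow up", so treatment does not stop at month 6.

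Control enters as an indicator that a participant "within clinic c is controlled at time t". The available text gives no blood pressure cut-off for it.

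**The concern.** Being uncontrolled at baseline is settled before randomisation, so restricting on it is harmless. Being controlled at 6 months is a response to the assigned arm. If the intervention works by month 6, its controlled subset includes people who would not have been controlled in the other arm, and the control arm's subset has no counterpart to them. Randomisation no longer balances the two groups being compared. Adjusting for chance baseline imbalance does not address selection that happens at month 6.

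The third model is also the only planned analysis of control at 12 months, because the second stops at month 6. A reader who asks whether control lasts would have this OR and no all-randomised counterpart. Section 4.5 narrows the subset further: a 6-month visit after month 7 counts as missing, so that participant cannot be classed as controlled at 6 months even with a valid 12-month reading.

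At stake is a supporting statement about whether benefit fades or persists, which the model could get wrong in either direction.

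**Working it through.** **The plan's own figure.** None is given for this model. The effect and SD used below do reproduce the Aim 1 sample size: 2 × [17.9 × (1.960 + 1.036) / 5.65]² ≈ 180 per arm, at the 85% power in the synopsis.

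**Inputs from the documents.** Difference between arms 5.65 mmHg (5.7 in the power sentence); pooled SD 17.9; control-arm decrease 11.6 mmHg; equal allocation.

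**Assumptions, not in the documents.** Control means SBP below 140; SD at each visit 17 to 17.9 (the plan's 17.9 is an SD of change, borrowed here); control-arm mean 142 to 145 at both visits; 6-to-12-month correlation ρ 0.4 to 0.7, equal in both arms; everyone uncontrolled at baseline. The cut-off is for calculation only.

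**Formulas.** For an arm with means m₆ and m₁₂ and common SD s:

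- P(controlled at 6) = Φ((140 − m₆)/s), and likewise at 12.
- P(controlled at both) = Φ₂((140 − m₆)/s, (140 − m₁₂)/s; ρ).
- q = P(controlled at both) / P(controlled at 6).
- Subset OR = odds of q, intervention over control.

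**One case in full.** Take s = 17.9, control mean 143.4 (an assumed baseline of 155 less 11.6) and ρ = 0.5.

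- Controlled at 6 months: control Φ(−3.4/17.9) = 0.425; intervention, 5.7 mmHg lower, Φ(2.3/17.9) = 0.551.
- Control arm: q = 0.2613/0.4247 = 0.615.
- Effect at 6 months, none at 12: intervention q = 0.3144/0.5511 = 0.571. Subset OR = (0.571/0.429)/(0.615/0.385) = 0.83. All-randomised 12-month OR = 1.00.
- Same effect at both visits: intervention q = 0.3860/0.5511 = 0.700. Subset OR = (0.700/0.300)/(0.615/0.385) = 1.46. All-randomised OR = (0.551/0.449)/(0.425/0.575) = 1.66.

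**Over the assumed ranges**

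| Scenario | All-randomised 12-month OR | Subset OR |
|---|---|---|
| 5.7 mmHg at 6 months, none at 12 | 1.00 | 0.72 to 0.87 |
| 5.7 mmHg at both | 1.66 to 1.71 | 1.39 to 1.53 |

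Between 38% and 46% of the control arm enter the subset, against 52% to 59% of the intervention arm.

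**Selection, or just a different population?** A simulation (2,000,000 per arm; effect 5.65; SD 17.9; cut-off 140 or 130; ρ 0.3 to 0.7) also computed the OR in people who would be controlled at 6 months under either arm, taking the effect as the same shift for everyone. With a constant effect that OR is 1.69 to 1.99, against a subset OR of 1.35 to 1.52. With an effect at 6 months only it is 1.00, against 0.71 to 0.90.

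**Does the direction hold?** Not always.

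- Persistent effect confined to the hardest-to-control 20% (28.25 mmHg each, so 0.20 × 28.25 = 5.65 on average; cut-off 140): subset OR 1.20, against 1.09 in the same people. The bias now favours the intervention, although the all-randomised OR is 1.67.
- No mean effect at 12 months but steadier pressures in the intervention arm (ρ 0.7 against 0.4): subset OR 1.32 to 1.46, against 1.00 in all randomised.
- No effect at either visit: subset OR 1.00, no bias.

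**The case against.** **Durability is a different question from the 12-month effect in everyone.** Maintenance of control once reached is a legitimate question, so a gap from the all-randomised OR is not by itself bias. That is right. The better benchmark is people who would be controlled at 6 months under either arm, and under a uniform effect the subset OR misses that benchmark too.

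**In the waning scenario the effect really has worn off.** This is also right, and the contrast ω₁₂ − ω₆ would show the full 5.7 mmHg loss. But a subset OR below 1 says more: that intervention participants hold control less well than control participants. In that scenario the same people have an OR of 1.00.

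**Intention to treat is glossed in terms of adherence.** Section 6 explains it by number of readings and pharmacist contacts, and the third model still analyses people by assigned arm. A reader might infer a flat contradiction. The text supports less: the model departs from the all-randomised basis that the statement implies.

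**The need is partly met already.** The first model estimates ω₆ and ω₁₂ without conditioning on response. This stands, and it is why the remedy is small. What is missing is a named contrast and any all-randomised comparison of 12-month control.

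**Conclusion.** The point holds for a supporting analysis. The third model's OR compares groups formed after randomisation by a response the plan expects treatment to change, and nothing in the plan adjusts for that or limits the model to description.

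A reader might infer that the model is biased against the intervention. The documents do not support that as a certainty. It follows under a roughly uniform effect, with the sizes tabulated above, but an effect concentrated in hard-to-control patients can reverse it. All magnitudes rest on the assumed cut-off, means, SD and correlation. The structural point does not depend on them, provided treatment affects control at 6 months.

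The primary 12-month SBP comparison is not conditioned on 6-month control. Blood pressure control is not among the listed secondary outcomes (12-month DBP, medication changes, cost). Neither those results nor the sample size is affected.

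**What to change.** In Section 6, Aim 1 Analysis:

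1. Make ω₁₂ − ω₆ from the specified linear mixed model the between-arm test of durability, reported with a confidence interval. Zero means the effect is unchanged from 6 to 12 months; a positive value means benefit lost. A non-significant result is not proof of persistence. As a rough guide, ignoring clustering, the 95% half-width with 180 per arm is 1.96 × √[4 × 17.9² × (1 − ρ)/180], or about 4.1 mmHg at ρ = 0.4 and 2.9 at ρ = 0.7.
2. Add a logistic mixed model for control at 12 months among everyone uncontrolled at baseline, in the form of the second model. State the definition of control that applies.
3. Keep the 12-month control percentages among those controlled at 6 months, by arm, as descriptive only.
4. If control at both 6 and 12 months is also reported, call it sustained control, not durability. It is a valid randomised comparison but carries the 6-month effect: with no effect at 12 months its OR is still 1.26 to 1.34 under the assumptions above (worked case: (0.3144/0.6856)/(0.2613/0.7387) = 1.30).

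The cost is SAP wording and one further model of a type already planned. No new data are needed, and the contrast needs no new model.

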Statistical Design and Power	
The analysis will be done on an intent-to-treat basis regardless of the number of reported BP readings or the number of pharmacist interactions with the participant.
 
Our primary outcome will be a comparison of mean SBP values at 12 months. We will use a linear mixed effects model with mean BP at 12 months as the outcome. We will use random effects for clinic and physician nested within clinic to account for practice heterogeneity between clinics and providers.
 
Based on prior work with the CAPTION trial, we expect a mean decrease in SBP of 17.3 (SD = 17.7) mmHg in the intervention arm and a decrease of 11.6 (SD = 18.2) mmHg in the control arm. We expect a difference of 5.65 mmHg between the groups with an expected pooled standard deviation of 17.9 with equal sized groups. In order to have 85% power to detect a difference of 5.7 mmHg or larger decrease in SBP with a Type I error rate of 5% and a standard deviation of 17.9 mmHg, we would need 180 subjects per arm or 360 subjects total.
 
In preliminary work in the CAPTION trial, 13.4% of control subjects dropped out or were lost to follow-up. 14.0% of subjects dropped out of the intervention arm during the first 9 months. In order to retain power after reasonable attrition rates over 12 months, we will recruit an additional 14% in each group to ensure we have at least 85% power. In addition, the sample size should slightly increase to accommodate the interim analyses. This increases our total sample size to 420.
 
One interim analysis is planned after outcome data is received and the results are reported to the Data Safety and Monitoring Board from the first half of the study. The interim monitoring method of Lan and DeMets will be used with O'Brien-Fleming alpha spending function for the interim analyses. Accordingly, type I error rate of 0.00305 for the interim analysis and 0.4695 will be used for the final analyses. The current sample size of 420 patients total accommodates the interim analyses.

Futility Analysis	To be determined by the Data and Safety Monitoring Board

Table of Contents

Study Protocol.....	1
Protocol Approval Page	2
Protocol Version and Amendment Tracking	3
Protocol Synopsis	4
Table of Contents.....	6
Table of Appendices	7
Abbreviations	8
1. Introduction.....	9
1.1 Background.....	9
1.2 Clinical Experience with the Study Intervention	9
2. Objectives, Aims, and Hypotheses	10
2.1 Objective.....	10
2.2 Aims and Hypotheses	10

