One interim analysis is planned after outcome data are received and the results are reported to the Data Safety and Monitoring Board from the first half of the study. The interim monitoring method of Lan and DeMets will be used with O'Brien-Fleming alpha spending function for the interim analyses. Accordingly, type I error rate of 0.00305 for the interim analysis and 0.4695 will be used for the final analyses. The current sample size of 420 patients total accommodates the interim analyses.

Aim 2 Analysis: The analysis will be done on an intent-to-treat basis regardless of the number of reported BPs or the number of pharmacist interactions with the subject. Our primary outcome will be the number of medication changes over 12 months in the control and intervention groups. We will use a GLMM based on the Poisson distribution with a log link function, and as in Aim 1 we will incorporate random effects for clinic and physician nested within clinic to account for practice heterogeneity between clinics and providers. As the observed treatment effects in those clusters are likely to be non-independent, we will include both random intercepts and random treatment effect for the intervention factor. Specifically, the model will be given as

$$\begin{aligned} \log(\mathbb{E}(Y_{cp})) &= \tau + \alpha_c + \gamma_{cp} + (\omega + \nu_c + \xi_{cp})X_{cp}, \\ (\alpha_c, \gamma_{cp})' &\stackrel{\text{iid}}{\sim} N(0, G_1), \\ (\nu_c, \xi_{cp})' &\stackrel{\text{iid}}{\sim} N(0, G_2), \end{aligned}$$

where Y_{cpi} is the number of medication changes for the i^{th} subject under the p^{th} provider within clinic c . The random effects incorporated into the final model will be chosen via AICc.

Power: Based on existing work, we expect an average of 4.9 medication changes in the intervention group (SD = 5.1) and an average of 1.1 medication changes in the control group (SD = 1.6). We would expect a difference of 3.8 changes per year with a pooled standard deviation of 3.8. In order to have 85% power to detect a difference of 3.8 or more changes with a Type I error rate of 5% and a standard deviation of 3.8, we would need 19 subjects per arm or 38 total. Considering both 14% loss to follow-up and adjusting the type I error rate for interim analysis, power of the study with our sample size of 420 will be more than adequate.

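### Section 6 claims 90% power for 180 per arm; the Synopsis gives 85% for the same inputs, and the arithmetic supports 85%

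*Combined protocol and SAP*

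**What the plan says.** The power calculation for the primary outcome appears twice in the combined protocol and SAP.

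- **Synopsis, Statistical Design and Power:** "In order to have 85% power to detect a difference of 5.7 mmHg or larger decrease in SBP".
- **Section 6, Aim 1 power paragraph:** "In order to have 90% power to detect a difference of 5.7 mmHg or larger decrease in SBP".

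Both continue "with a Type I error rate of 5% and a standard deviation of 17.9 mmHg", and both conclude "we would need 180 subjects per arm or 360 subjects total". Both take the same CAPTION-based expectations: falls in SBP of 17.3 and 11.6 mmHg, an expected difference of 5.65 mmHg, and a pooled SD of 17.9. The power figure is the only input that differs.

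The paragraph after the 90% statement in Section 6 covers attrition: "we will recruit an additional 14% in each group to ensure we have at least 85% power". It brings the total to 420. The Aim 2 power paragraph also plans at 85%: "In order to have 85% power to detect a difference of 3.8 or more changes".

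**The concern.** Once the difference, SD, type I error rate and sample size are fixed, power is fixed too. Two values for the same set of inputs mean that one is wrong. Section 6 also disagrees with itself, because one paragraph claims 90% and the next sets out to preserve at least 85%.

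This is the design power for the primary outcome, in the section that governs the analysis. Someone relying on the 90% sentence would put the type II error at 10%. That affects how a null result is read. It could also mislead the DSMB, to which the Synopsis leaves the futility analysis, if the board took its design power from Section 6.

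**Working it through.** **Inputs.** From the Aim 1 power paragraph and the matching Synopsis text: difference δ = 5.7 mmHg in the power sentence (5.65 expected), SD σ = 17.9, type I error 5%, equal arms, n = 180 per arm, 14% attrition, 420 in total. Sidedness is not stated, so both readings are tried.

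**Step 1. Power at 180 per arm, two-sided 5%.**

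- Standard error: σ√(2/n) = 17.9 × √(2/180) = 1.887.
- Normal approximation: power = Φ(δ/SE − 1.960) = Φ(5.7/1.887 − 1.960) = Φ(1.061) = 85.6%.
- The t-test gives 85.4%. At 5.65 mmHg the two figures are 85.0% and 84.8%.

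This reproduces the Synopsis figure of 85% and not the 90% in Section 6.

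**Step 2. Sample size for each power, two-sided 5%.** n per arm = 2(1.960 + z_power)²σ²/δ², with z = 1.036 for 85% and 1.282 for 90%. The table gives the t-test values.

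| Target power | n per arm at 5.7 mmHg | n per arm at 5.65 mmHg |
|---|---|---|
| 85% | 178.1 | 181.2 |
| 90% | 208.2 (so 209) | 211.9 (so 212) |

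The stated 180 lies between the two 85% values. It is about 30 per arm short of the 90% values, which is too much for rounding.

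**Step 3. Could the test be one-sided at 5%?** At 5.7 mmHg, 180 per arm would then give 91.5% power, but 90% would need only 169.6 per arm (172.6 at 5.65). Neither yields 180. Two other figures in Section 6 show which convention was used.

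- Interim analysis: "type I error rate of 0.00305 for the interim analysis". The Lan-DeMets O'Brien-Fleming-type function spends 2[1 − Φ(z₁₋ₐ/₂/√t)] on one side, where a is that side's alpha. At half information (t = 0.5), two sides at a = 0.025 spend 2 × 2[1 − Φ(2.241/√0.5)] = 0.00305. One side at a = 0.05 spends 2[1 − Φ(1.960/√0.5)] = 0.00557. Only two-sided 5% matches.
- Aim 2: "we would need 19 subjects per arm or 38 total". The standardised difference is 3.8/3.8 = 1. The t-test sample sizes are 18.97 (two-sided 85%), 15.1 (one-sided 85%), 17.8 (one-sided 90%) and 22.0 (two-sided 90%). Only two-sided 85% rounds up to 19.

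**Step 4. Which calculation produced 420?** 180/(1 − 0.14) = 209.3, or 210 per arm and 420 in total. Starting from 209 per arm for 90% power, the same step gives 209/0.86 = 243.02, or 244 per arm and 488 in total. The enrolment target was built on the 180-per-arm figure.

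**Step 5. Power of the trial as planned.** Completers: 420 × 0.86/2 = 180.6 per arm. By normal approximation throughout, so that the figures compare like with like:

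| | 5.7 mmHg | 5.65 mmHg |
|---|---|---|
| No interim look | 85.7% | 85.1% |
| One look at half information, 0.00305 spent, two-sided 5% overall | 85.6% | 84.9% |

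The interim look costs about 0.1 percentage point. With no attrition at all, 210 per arm would give 90.2% at 5.7 mmHg and 89.7% at 5.65 mmHg (t-test).

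**The case against.** The best defence is that a careful reader would not be misled for long. The paragraph after the 90% statement, the Synopsis and the Aim 2 paragraph all say 85%, and no test, estimate or decision rule uses the 90%. This is fair, and it limits the weight of the point. It does not make the sentence correct.

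A second defence is that the Section 2.2 hypotheses are directional and the Aim 1 text does not state sidedness. Under a one-sided 5% test, 180 per arm would exceed 90% power. The sentence, however, presents 180 as the number required for 90%, and on that reading the requirement is 170. One-sided testing also conflicts with the interim alpha and the Aim 2 figure, and it cannot account for the Synopsis giving 85% on the same inputs.

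A third is that 420 subjects do give about 90%. That holds only if almost all 210 per arm are evaluable, whereas the plan allows for 14% loss. Section 6 attaches the 90% to 180 per arm.

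One caution stands. The documents never say which figure is the slip. If 90% was really intended, 420 would be too few after the planned attrition. The evidence favours 85%, but the sponsor should confirm it.

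**Conclusion.** The concern holds. Section 6 states 90% where its own inputs give about 85%: 85.4% at 5.7 mmHg and 84.8% at 5.65 mmHg. The type II error is about 15%, not 10%. The error lies in the stated power; the sample size, alpha and analysis model are unaffected.

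The conclusion rests on a two-sided 5% test, which is inferred from the interim alpha and the Aim 2 sample size. It also rests on a simple two-sample comparison with SD 17.9, the only basis that the plan's power text supplies. The planned mixed model, with clinic and physician effects, was not evaluated here. At the expected 5.65 mmHg the design meets 85% only to rounding.

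**What to change.** In the Aim 1 power paragraph of Section 6, change 90% to 85%, after the sponsor confirms that 85% is the intended target. State in both Section 6 and the Synopsis that the type I error rate is two-sided 5%. The cost is one figure and one added word in each place. On the 85% target no extra enrolment is needed, and alpha and the analysis stay as they are. If the sponsor says that 90% was meant, the sample size itself would have to be revisited.

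### The final-analysis significance level is printed as 0.4695; applied literally, the overall type I error is about 47%, and restoring the lost zero (0.04695) still does not give the correct final boundary

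*Combined protocol and SAP*

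**What the plan says.** Section 6 (Statistical Design and Power) provides for a single interim analysis on data from the first half of the study, reported to the monitoring board. The method is named: "The interim monitoring method of Lan and DeMets will be used with O'Brien-Fleming alpha spending function for the interim analyses". The levels follow directly: "type I error rate of 0.00305 for the interim analysis and 0.4695 will be used for the final analyses". The Statistical Design and Power entry of the Protocol Synopsis gives the same two figures in the same words.

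The sample size rests on a different error rate. The Aim 1 power paragraph of Section 6 works "with a Type I error rate of 5% and a standard deviation of 17.9 mmHg, we would need 180 subjects per arm or 360 subjects" in total, and the Synopsis also uses 5%.

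The plan does not give 0.04695, a final critical value, the sidedness of the test or an explicit information fraction anywhere. Nothing in it corrects the printed final level.

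**The concern.** A final level of 0.4695 cannot coexist with an overall type I error of 5%. It is also the decision threshold for the primary comparison of 12-month SBP. If it were applied as printed, an ineffective intervention would be declared effective almost half the time.

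Most readers will see a misprint, but they can repair it in more than one way. Moving the decimal point gives 0.04695, computing the boundary gives 0.0490, and falling back on the power paragraph gives 0.05. A primary p-value between 0.04695 and 0.05 would be significant under some of these readings and not under others. If the choice is made after the data are seen, it is post hoc.

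**Working it through.** **Inputs.** From Section 6: overall alpha 0.05; one interim look after the first half of the study; Lan-DeMets with O'Brien-Fleming-type spending; stated levels 0.00305 and 0.4695. For power: 180 per arm, SD 17.9 mmHg, and a difference of 5.7 mmHg (the power sentence) or 5.65 mmHg (the expected difference). Two assumptions are not in the text: the test is two-sided, and the information fraction at the look is t = 0.5.

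**Step 1: reproduce the interim level.** Spend 0.025 on each side:

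α(t) = 4 × [1 − Φ(z₀.₉₈₇₅ / √t)]

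With z₀.₉₈₇₅ = 2.2414 and √0.5 = 0.7071, the argument is 3.170, so α(0.5) = 4 × 0.000763 = 0.00305. The plan's figure reproduces, with interim boundary |z| = 2.963. Spending 0.05 as a whole would give 0.00558, and the classic O'Brien-Fleming boundary would give 0.00517. The match therefore supports the two-sided, per-side, 50% reading.

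**Step 2: source of the final figure.** Alpha left to spend: 0.05 − 0.00305 = 0.04695. The printed 0.4695 has the same digits with one zero missing.

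**Step 3: the correct final threshold.** Under the null hypothesis the interim and final statistics are bivariate normal with correlation √0.5. Solve for c₂ in

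P(|Z₁| > 2.963 or |Z₂| > c₂) = 0.05.

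The result is c₂ = 1.969, a nominal two-sided level of 0.0490. It exceeds 0.04695 because some final-look rejections would already have occurred at the interim and should not be charged twice.

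**Step 4: overall type I error by final level** (interim at 0.00305, numerical integration). The last column is the smallest observed difference that would be called significant, c₂ × SE, with SE = 17.9 × √(2/180) = 1.887 mmHg.

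| Final level | c₂ | Overall type I error | Smallest significant difference |
|---|---|---|---|
| 0.4695 (as printed) | 0.723 | 46.95% | 1.4 mmHg |
| 0.04695 (zero restored) | 1.987 | 4.80% | 3.7 mmHg |
| 0.0490 (correct boundary) | 1.969 | 5.00% | 3.7 mmHg |

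A simulation of 4 million trials agrees: 46.9%, 4.8% and 5.0%. Leaving the final test at 0.05 after the interim look would give 5.10%.

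**Step 5: power cost of using 0.04695 instead of 0.0490** (180 per arm, SD 17.9, interim rejections counted).

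- Difference 5.7 mmHg: 85.4% with 0.0490 and 85.0% with 0.04695.
- Difference 5.65 mmHg: 84.8% and 84.4%.

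The loss is about 0.4 percentage points either way.

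**Step 6: dependence on timing.** The same spending function at other information fractions gives:

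| t | Interim level | Final nominal level |
|---|---|---|
| 0.4 | 0.0008 | 0.0497 |
| 0.5 | 0.00305 | 0.0490 |
| 0.6 | 0.0076 | 0.0476 |

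**The case against.** The strongest reply is that this is a visible misprint. The spending method and the 5% overall rate are both stated, and the digits point straight to 0.04695, so nobody would run the test at 0.4695. That makes the 47% conditional on literal use. It does not make the text safe, because the wrong figure stands twice in current text, nothing corrects it, and the repair is not unique.

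A second reply is that the sentence speaks of a type I error rate just after naming a spending function. Read as alpha spent per look, 0.00305 + 0.04695 = 0.05 is exactly right, and criticising 0.04695 as a threshold attacks a use the plan never states. This is partly fair. That reading is open, and the figure is correct under it. But the text says the rates will be used for the analyses, and the plan gives no separate boundary. On the spending reading, the threshold is simply missing.

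Three further points stand. Using 0.04695 as the threshold is conservative and costs little, so only the decimal error carries the seriousness. The value 0.0490 depends on two-sided testing at 50% information, which the text implies but does not state. And adopting Lan-DeMets already implies boundaries computed at the actual fraction, so saying so clarifies the plan and does not correct an arithmetic error.

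**Conclusion.** The plan is wrong as written and must be corrected. The printed final level contradicts the plan's own 5% and, if applied, gives an overall type I error of 46.95%. The natural repair, 0.04695, is the alpha increment and not the nominal threshold. Used as a threshold it gives 4.80% overall and loses about 0.4 points of power, which is minor and errs on the safe side. The threshold that uses the full 5% is 0.0490.

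These figures assume a two-sided test and an interim look at exactly 50% information. The exact reproduction of 0.00305 supports both assumptions.

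**What to change.** In the Protocol Synopsis and in Section 6, replace 0.4695 with a final nominal two-sided significance level of 0.0490 (critical value 1.969). State alongside it that the interim level is 0.00305 at 50% information and that cumulative two-sided alpha is 0.05. If the sponsor wishes to keep 0.04695, label it as alpha spent at the final look and give the 0.0490 boundary separately.

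Add one sentence that defines the information fraction as the share of planned 12-month SBP outcomes available at the look, and that says both boundaries are recomputed from the O'Brien-Fleming spending function at the fraction actually reached.

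The cost is a short wording correction in two places. The sample size and trial conduct do not change. It should be made before any unblinded look at the outcome data.
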